1 SAP SYNOPSIS

TITLES OF STUDY: A Phase 2 Randomized, Double-Blind, Placebo-Controlled Clinical Trial to Evaluate the Safety and Efficacy of vosoritide in Infants and Young Children with Achondroplasia, Age 0 to < 60 Months.

PROTOCOL NUMBER: 111-206

STUDY SITES: Approximately 10-15 clinical centers worldwide

PHASE OF DEVELOPMENT: Phase 2

OBJECTIVES:

The primary objectives of the study are to:

- Evaluate the safety and tolerability of vosoritide in children age 0 to < 60 months with Achondroplasia (ACH)
- Evaluate the effect of vosoritide on change from baseline in standing height/body length Z-score

The secondary objectives of the study are to:

- Evaluate the effect of vosoritide on change from baseline in standing height/body length, annualized growth velocity (AGV), and upper: lower segment body ratio throughout the 52-weeks of the study
- Evaluate the effect of vosoritide on other growth parameters and body proportions
- Evaluate the effect of vosoritide on bone morphology/quality by X-ray and dual X-ray absorptiometry (DXA)
- Evaluate the Pharmacokinetics (PK) of vosoritide in children age 0 to < 60 months with ACH
- Evaluate hip function
- Evaluate for hip, thigh, or knee pain, or change in gait
- Evaluate the effect of vosoritide on health-related quality of life (HRQoL), developmental status, and functional independence using age-specific QoL and functional independence questionnaires (Bayley Scales of Infant and Toddler Development, Third edition [Bayley-III], Activity of Daily Living and Functional Independence Measure (Wee-FIM), Infant Toddler Quality of Life Questionnaire (ITQOL), Child Behavior Checklist (CBCL))
- Evaluate immunogenicity of vosoritide and assess impact on safety, PK, and efficacy measures
- Evaluate the effect of vosoritide on bone metabolism and vosoritide pharmacodynamic (PD) biomarkers
- Evaluate the effect of vosoritide on sleep apnea
- Evaluate the effect of vosoritide on skull and brain morphology, including foramen magnum, ventricular and brain parenchymal dimensions

Study 111-206 SAP

- Describe the incidence of surgical interventions, including cervical decompression, adenotonsillectomy, and tympanostomy

The exploratory objectives of the study are to:

- Document physical and phenotypic changes with clinical photography (optional)
- Evaluate genomic biomarkers (optional).

The exploratory objectives of the study are optional and will not be addressed in this SAP.

STUDY DESIGN AND PLAN: Study 111-206 is a phase 2 randomized, double-blind, placebo-controlled clinical trial of vosoritide in infants and younger children with a diagnosis of ACH.

Approximately 70 Subjects will be enrolled into 3 age cohorts: $n \geq 30$ total for aged ≥ 24 to < 60 months, $n \geq 20$ total for aged ≥ 6 to < 24 months, and $n \geq 20$ total for aged 0 to < 6 months.

There will be 3 sentinel subjects for each cohort, and the rest of subjects will be randomized 1:1 to treatment or placebo control and stratified by age for Cohorts 1 and 2.

All subjects who complete the 111-206 study will be eligible to receive vosoritide in the extension study 111-208 after the Week 52 visit.

ANALYSIS POPULATIONS:

The Full Analysis Set (FAS) is defined according to the intent-to-treat principle and includes all enrolled sentinel and randomized subjects with a signed informed consent.

The Per-Protocol (PP) population is defined as a subset of the FAS population who completed the treatment originally allocated (i.e., always received the assigned treatment), with a standing height/body length assessment at Week 52 following the protocol window, and with treatment compliance of at least 80%.

The Safety Population is a subset of the FAS who receive at least one dose of vosoritide or placebo in this study.

The PK Population is defined as all sentinel subjects and subjects randomized to vosoritide treatment group, who received at least one dose of vosoritide in this study and have at least one evaluable PK concentration.

The Immunogenicity Population is defined as all subjects in the Safety Population who have at least one evaluable immunogenicity sample.

STUDY ENDPOINTS AND ANALYSES:

Efficacy endpoints and analysis:

The primary efficacy endpoint is change from baseline in standing height/body-length Z-score at Week 52.

The key secondary efficacy endpoints include change from baseline at Week 52 in standing height/body length, AGV, and upper to lower body ratio. Other secondary efficacy endpoints include biomarker samples to evaluate the effect of vosoritide on bone metabolism, vosoritide pharmacodynamic biomarkers, growth parameters and body proportions, sleep apnea, skull and brain morphology, and clinical outcome assessments (developmental/functional/HRQoL status).

**Study 111-206 SAP**

In addition to the summary statistics analyses for efficacy endpoints, model-based analysis will be conducted for change from baseline at Week 52 in standing height/body length Z-Score, standing height/body length, AGV, and upper to lower body ratio for all cohorts overall and/or by cohort, as appropriate.

Safety endpoints and analyses:

Adverse events (AEs) will be coded using Medical Dictionary for Regulatory Activities (MedDRA) Version 24.1 and presented by System Organ Class (SOC) and Preferred Term (PT). Summaries of AE's will include all AE's, serious adverse events (SAEs) and events of interest (EOI).

Clinical laboratory tests will be summarized descriptively. Shift tables tabulating Common Terminology Criteria for Adverse Events (CTCAE) severity grade at baseline versus worst post-baseline grade will be provided.

Vital signs will be summarized descriptively. Shift tables tabulating shifts from pre-dose (diastolic blood pressure (BP) < 40 mmHg, diastolic BP \geq 40mmHg) to lowest post-injection value (diastolic BP \geq 40mmHg) will be provided. Additional shift tables will describe similar pre/post injection shifts in vital signs.

X-rays and DXA will be performed on the extremities and spine to evaluate changes in bone morphology and quality.

Anti-vosoritide immunogenicity assessments will be summarized descriptively. Behavioral assessments with the CBCL will be summarized descriptively.

Other analyses:

Additional analyses will be conducted as appropriate to evaluate the impact of the COVID-19 pandemic on the study conduct.

Study 111-206 SAP
TABLE OF CONTENTS

1	SAP SYNOPSIS	2
2	APPROVAL (SIGNATURE AND DATE).....	9
3	LIST OF ABBREVIATIONS	10
4	INTRODUCTION	12
4.1	Objectives of Study	12
4.2	Study Design	13
4.3	Study Populations	15
4.4	Study Dosage and Administration	15
4.5	Sample Size Determination.....	15
4.6	Blinding and Randomization Methods	15
4.6.1	Blinding Method.....	15
4.6.2	Randomization Method	15
4.7	Interim Analysis.....	16
5	GENERAL ANALYSIS CONSIDERATIONS	17
5.1	Analysis Populations.....	19
5.1.1	Full Analysis Set	19
5.1.2	Per-Protocol.....	19
5.1.3	Safety.....	19
5.1.4	PK.....	19
5.1.5	Immunogenicity.....	20
5.2	Pooling of Data from Sites with Small Enrollment	20
5.3	Study Day Derivation.....	20
5.4	Visit Windows for Analysis.....	20
5.5	Handling of Dropouts and Missing Data	22
5.5.1	Partial Dates	22
6	SUBJECT DISPOSITION	24
7	DISCONTINUATION AND COMPLETION	25
8	PROTOCOL EXEMPTIONS AND DEVIATIONS	26

3 LIST OF ABBREVIATIONS

Abbreviation	Definition
µg/kg	microgram/kilogram
ACH	achondroplasia
ADA	anti-drug antibody
AE	adverse event
AGV	annualized growth velocity
ANCOVA	Analysis of covariance
ANP	atrial natriuretic peptide
ATC	Anatomical Therapeutic Chemical
BMC	bone mineral content
BMD	bone mineral density
BMI	body mass index
BMN	BioMarin
BNP	brain natriuretic peptide
BP	blood pressure
BSAP	bone-specific alkaline phosphatase
CBCL	Child Behavior Checklist
CDC	Centers for Disease Control and Prevention
CM	concomitant medication
CRF	case report form
cGMP	cyclic guanosine monophosphate
CNP	C-type natriuretic peptide
CSR	clinical study report
CTCAE	Common Terminology Criteria for Adverse Events (v4.03)
CTX-II	C-terminal telopeptide of cross-linked collagen type II
DBL	database lock
DMC	data monitoring committee
DXA	dual x-ray absorptiometry
ECG	electrocardiogram
ECHO	echocardiogram
eCRF	electronic case report form
EMA	European Medicines Agency
FAS	full analysis set
FDA	Food and Drug Administration
JNDA	Japan New Drug Application

Study 111-206 SAP

HPA	hypothalamic pituitary adrenal
HRQoL	health-related quality of life
ISR	injection site reaction
ITQoL	Infant Toddler Quality of Life Questionnaire
IXRS	interactive web or voice response system
MAA	Marketing Authorization Application
MedDRA	Medical Dictionary for Regulatory Activities
NAb	neutralizing antibody
NCI	National Cancer Institute
NDA	New Drug Application
PD	pharmacodynamic
PK	pharmacokinetic
PP	per protocol
PT	preferred term
QTc-F	Fridericia's corrected QT interval
SAE	serious adverse event
SAP	statistical analysis plan
SC	Subcutaneous
SCFE	slipped capital femoral epiphysis
SD	standard deviation
SDS	standard deviation score
SE	standard error
SMQ	Standardized MedDRA query
SOC	system organ class
TAb	total anti-drug antibody
TEAE	treatment-emergent adverse event
TLGs	tables, listings, and graphs
WeeFIM	Activity of Daily Living and Functional Independence Measure
WHO	World Health Organization

**Study 111-206 SAP****4 INTRODUCTION**

Study 111-206 (original protocol effective date: 06 December 2017) is a Phase 2 randomized, double-blind, placebo-controlled clinical trial to evaluate the safety and efficacy of vosoritide in infants and young children with ACH, aged 0 to < 60 months.

This final SAP is based on Amendment 2 of Study 111-206 (date: 08 February 2019). It describes the analyses and evaluations that will be provided for the final clinical study report (CSR).

Where there are major differences between the protocol-defined analyses, and the SAP-defined analyses, these will be identified in the SAP. The SAP-defined analyses prevail.

4.1 Objectives of Study

The primary objectives of study are to:

- Evaluate the safety and tolerability of vosoritide in children age 0 to < 60 months with ACH
- Evaluate the effect of vosoritide on change from baseline in standing height/body length Z-score (height Z-Score may be used interchangeable)

The secondary objectives of study are to:

- Evaluate the effect of vosoritide on change from baseline in standing height/body length, AGV, and upper: lower body segment ratio throughout the 52 weeks of the study
- Evaluate the effect of vosoritide on other growth parameters and body proportions
- Evaluate the effect of vosoritide on bone morphology/quality by x-ray and DXA
- Evaluate the PK of vosoritide in children age 0 to < 60 months with ACH
- Evaluate hip function
- Evaluate for hip, thigh, or knee pain, or change in gait
- Evaluate the effect of vosoritide on HRQoL, developmental status, and/functional independence using age-specific QoL and functional independence questionnaires/QOL status (Bayley-III), Wee-FIM, ITQOL, and CBCL
- Evaluate immunogenicity of vosoritide and assess impact on safety, PK, and efficacy measures
- Evaluate the effect of vosoritide on bone metabolism and vosoritide PD biomarkers
- Evaluate the effect of vosoritide on sleep apnea

Study 111-206 SAP

- Evaluate the effect of vosoritide on skull and brain morphology, including foramen magnum, ventricular and brain parenchymal dimensions
- Describe the incidence of surgical interventions, including cervical decompression, adenotonsillectomy, and tympanostomy

The exploratory objectives are to:

- Documental physical and phenotypic changes with clinical photography (optional)
- Evaluate genomic biomarkers (optional)

The exploratory objectives of the study are optional and will not be addressed in this SAP.

4.2 Study Design

Study 111-206 is a phase 2 stratified randomized, double-blind, placebo-controlled clinical trial of vosoritide in infants and younger children with a diagnosis of ACH.

Subjects aged ≥ 6 months to < 60 months old who have documented ACH confirmed by genetic testing; at least a 6-month period of pretreatment growth assessment in Study 111-901 immediately before study entry; and who meet the study eligibility criteria, will participate. Eligible subjects ranging from 0 months to < 3 months old may enroll directly into 111-206 and have a minimum of 3 months of pre-treatment observation prior to commencing treatment with investigational product or may enroll in 111-901 for a minimum of 3 months of pretreatment growth assessment immediately before roll-over to 111-206.

Approximately 70 subjects will be enrolled at approximately 10-15 clinical centers worldwide.

Subjects will be enrolled into 3 age cohorts based on age at study screening starting with the eldest population. Within Cohorts 1 and 2, subjects will be stratified by age:

- Cohort 1 – children aged ≥ 24 to < 60 months ($n \geq 30$ total: 3 sentinel subjects who receive vosoritide, and at least 27 additional subjects randomized 1:1 to treatment or placebo control), stratified by age (≥ 24 months to < 36 months and ≥ 36 months to < 60 months)
- Cohort 2 – children aged ≥ 6 to < 24 months ($n \geq 20$ total: 3 sentinel subjects who receive vosoritide, and at least 17 additional subjects randomized 1:1 to treatment or placebo control), stratified by age (≥ 6 months to < 15 months and ≥ 15 months to < 24 months)

Study 111-206 SAP

- Cohort 3 – children aged 0 to < 6 months ($n \geq 20$ total: 3 sentinel subjects who receive vosoritide, and at least 17 additional subjects randomized 1:1 to treatment or placebo control). Treatment begins at ≥ 3 months to < 6 months after 3 months of observation.

[figure not shown]
Sentinel subjects from each cohort will be enrolled, treated with vosoritide, and studied for short-term safety and PK data. After the sentinel data are evaluated within a cohort additional recruited subjects will be randomized to receive vosoritide or placebo subcutaneous daily (1:1 ratio) for 52 weeks.

As subjects age on study, they will be administered the dose determined to be appropriate for their current age as follows:

All sentinel and randomized subjects in Cohort 1 received 15 $\mu\text{g}/\text{kg}$ dose. Sentinel subjects in Cohort 2 initially received 15 $\mu\text{g}/\text{kg}$ dose and the dose was escalated to 30 $\mu\text{g}/\text{kg}$ while they remained < 24 months of age following review of PK data as per protocol. All randomized subjects in Cohort 2 will receive 30 $\mu\text{g}/\text{kg}$ dose while they remained < 24 months of age. All sentinel and randomized subjects in Cohort 3 received 30 $\mu\text{g}/\text{kg}$ dose while they remained < 24 months of age. The dose for all sentinel and randomized subjects in Cohorts 2 and 3 will be adjusted to 15 $\mu\text{g}/\text{kg}/\text{day}$ after they turn 24 months old.

The 111-206 study design is presented in [Figure 4.2.1](#). All subjects who complete the 111-206 study will be eligible to receive vosoritide in the extension study 111-208 after the Week 52 visit.

Figure 4.2.1: Study Design

Study 111-206 SAP

4.3 Study Populations

Subjects aged 0 to < 60 months old, with documented ACH confirmed by genetic testing, and who meet the study eligibility criteria will participate.

For additional criteria for selection of study population, please refer to inclusion and exclusion criteria for the protocol.

4.4 Study Dosage and Administration

In Study 111-206, sentinel subjects in Cohort 1 will receive an initial daily dose of 15 µg/kg. All available safety and PK data will be reviewed after 3 sentinel subjects reach Day 8. If the criteria for dose adjustment are met, the 3 sentinel subjects will be started on the new adjusted dose at their next scheduled visit and the remainder of the subjects in the age cohort will also be enrolled starting at the new adjusted dose. The 3 sentinel subjects for the second and third cohorts will be evaluated similarly to the sentinel subjects in the first cohort for potential dose adjustment. Additional sentinels may be added to any cohort if needed for additional safety and/or PK assessment.

4.5 Sample Size Determination

Approximately 70 subjects aged 0 to < 60 months at study entry will participate in 111-206. No formal sample size calculations were performed. The number of subjects is considered appropriate to evaluate the safety and efficacy of vosoritide in the target population.

4.6 Blinding and Randomization Methods

4.6.1 Blinding Method

This is a placebo-controlled, double-blind study. Blinding is strictly maintained during the study and a study specific masking plan describes how potentially unblinding data are handled during the lifetime of the study. The study will remain blinded until after all data has been entered, and the final database has been locked.

4.6.2 Randomization Method

The centralized randomization with stratification is managed by an external vendor, using IXRS technology.

Subjects will be enrolled into 3 age cohorts based on age at study screening starting with the eldest population. In each cohort, eligible subjects will be randomized in a 1:1 ratio to vosoritide or placebo after 3 sentinel subjects are treated. Cohorts 1 and 2 will be stratified by age. Subjects are randomized separately within each cohort in Japan.

**Study 111-206 SAP****4.7 Interim Analysis**

No formal interim futility/efficacy analyses are planned. Two informal interim analyses including data from both Studies 111-206 and 111-208 were performed for selected domains: one for New Drug Application (NDA) to Food and Drug Administration (FDA) and marketing authorization applications (MAA) to European Medicines Agency (EMA), dated 18 December 2019, and another for Japan New Drug Application (JNDA), dated 11 November 2020. For these analyses, subjects remained blinded and no efficacy data was analyzed for the randomized subjects nor post baseline listings except for serious adverse events.

In addition to safety and PK monitoring by BioMarin Personnel, an independent data monitoring committee (DMC) will act in an advisory capacity to BioMarin to monitor subject safety and PK of subjects who participate in the study. A DMC review will occur to evaluate all available safety and PK data after the sentinel subjects complete 12 weeks of dosing, and DMC will make recommendations for stopping or continuing the study, and endorse dose adjustments if needed, based on pre-specified criteria. DMC data review meetings occur approximately every 6 months during the course of the study.

Study 111-206 SAP

5 GENERAL ANALYSIS CONSIDERATIONS

The analyses described in this final SAP are based on Amendment 2 of the protocol (date: 08 February 2019).

Individual subject data that is reflected in data summaries will be provided in listings. Unless otherwise specified, all listings will be by cohort, by sentinel/randomized subjects, by treatment group, and ordered by subject number, where subject number includes the site number.

Unless otherwise specified, summary tables for efficacy variables will use format in [Table 5.1](#), [Table 5.2](#), and [Table 5.3](#) for Cohorts 1, 2, and 3, respectively. Summary tables for safety variables will be separated by cohort and overall by treatment group using format in [Table 5.4](#).

Table 5.1: Format for Efficacy Summary Analyses for Cohort 1

Sentinel	Randomized						All Vosoritide Treated*		
	Vosoritide			Placebo					
	≥ 24 to < 36 months	≥ 36 to < 60 months	Over all	≥ 24 to < 36 months	≥ 36 to < 60 months	Over all	≥ 24 to < 36 months	≥ 36 to < 60 months	Over all

*All vosoritide treated includes sentinel subjects and randomized subjects who received vosoritide.

Table 5.2: Format for Efficacy Summary Analyses for Cohort 2

Sentinel	Randomized						All Vosoritide Treated*		
	Vosoritide			Placebo					
	≥ 6 to < 15 months	≥ 15 to < 24 months	Over all	≥ 6 to < 15 months	≥ 15 to < 24 months	Over all	≥ 6 to < 15 months	≥ 15 to < 24 months	Over all

*All vosoritide treated includes sentinel subjects and randomized subjects who received vosoritide.

Table 5.3: Format for Efficacy Summary Analyses for Cohort 3

Sentinel	Randomized		All Vosoritide Treated*
	Vosoritide	Placebo	

*All vosoritide treated includes sentinel subjects and randomized subjects who received vosoritide.

	Study 111-206 SAP
---	--------------------------

Table 5.4: Format for Safety Summary Analyses for Cohort 1*

Sentinel	Randomized		All Vosoritide Treated**
	Vosoritide	Placebo	

* Cohort 2, Cohort 3, and Overall will have the same format as Cohort 1.

**All vosoritide treated includes sentinel subjects and randomized subjects who received vosoritide.

Baseline growth measures (other than AGV, baseline AGV is defined in Section 14.3.2) and baseline weight are those assessed on Day 1 of dosing, regardless of timing relative to dosing. (Note: If no assessments are available, then the baseline assessment will be the last non-missing assessment prior to Day 1). Baseline assessments are the last non-missing on-study assessments prior to administration of study treatment. Change from baseline is calculated as: (post-baseline value – baseline value); Percent change from baseline is calculated as: $(\text{[post-baseline value} - \text{baseline value]}/\text{baseline value}) \times 100$.

The screening visit will not be presented in descriptive summaries over time. When the analysis windows have been applied (see Section 5.4), data collected at the screening visit may be included in the baseline assessment. All assessments will be listed, but only those assessments assigned to visits according to the windows applied (see Section 5.4) will be summarized in tables or graphically. Exceptions to this are summaries of the worst post-baseline laboratory data in shift tables where all assessments are considered.

Unless otherwise specified, summary statistics n, mean, standard deviation (SD), median, 25th and 75th percentile, minimum, and maximum will be provided for numerical variables. The mean, 25th percentile, median, 75th percentile, and estimates of precision (e.g. SD, confidence interval) will be displayed to one more decimal place than the collected data. Minimum and maximum values will be presented to the same decimal places as the collected data. The number of decimal places to which endpoints are reported follow the project programming standards.

Number and percentage will be provided for categorical variables. When summarizing categorical data, for mutually exclusive categories, the sum of the individual categories, including a separate “Missing” category, should equal 100%. Unless otherwise specified, if categories have no data, then they will not be displayed.

All statistical analyses will be performed using SAS® version 9.4 or a later release (SAS Institute, North Carolina, USA) and results be presented in the form of tables, listings, and graphs (TLGs). All statistical analyses, including dataset creation and output generation, will

**Study 111-206 SAP**

be performed by Biostatistics and Statistical Programming personnel of BioMarin's Biometrics department.

5.1 Analysis Populations**5.1.1 Full Analysis Set**

The Full Analysis Set (FAS) is defined according to the intent-to-treat principle and includes all enrolled sentinel and randomized subjects with a signed informed consent. The FAS will be the main analysis population for summaries and/or analyses described in the SAP, including but not limited to summaries and/or analyses of demographics, baseline characteristics, dispositions, and all efficacy endpoints.

All listings, excluding screen failures, will be produced on the FAS.

5.1.2 Per-Protocol

The Per-Protocol (PP) population is defined as a subset of the FAS population who completed the treatment originally allocated (i.e., always received the assigned treatment (vosoritide or placebo)), with a standing height/body length assessment at Week 52 following protocol window, and with treatment compliance of at least 80%.

The PP population will be used for sensitivity analysis of the primary and key secondary efficacy endpoints only.

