All sentinel and randomized subjects in Cohort 1 received 15 µg/kg dose. Sentinel subjects in Cohort 2 initially received 15 µg/kg dose and the dose was escalated to 30 µg/kg while they remained < 24 months of age following review of PK data as per protocol. All randomized subjects in Cohort 2 will receive 30 µg/kg dose while they remained < 24 months of age. All sentinel and randomized subjects in Cohort 3 received 30 µg/kg dose while they remained < 24 months of age. The dose for all sentinel and randomized subjects in Cohorts 2 and 3 will be adjusted to 15 µg/kg/day after they turn 24 months old.

The 111-206 study design is presented in [Figure 4.2.1](#). All subjects who complete the 111-206 study will be eligible to receive vosoritide in the extension study 111-208 after the Week 52 visit.

Figure 4.2.1: Study Design

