5.1.2 Per-Protocol

The Per-Protocol (PP) population is defined as a subset of the FAS population who completed the treatment originally allocated (i.e., always received the assigned treatment (vosoritide or placebo)), with a standing height/body length assessment at Week 52 following protocol window, and with treatment compliance of at least 80%.

The PP population will be used for sensitivity analysis of the primary and key secondary efficacy endpoints only.

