12 COMPLIANCE

Treatment compliance will be calculated based on the study treatment preparation and study treatment administration records captured in the eCRF, and summarized separately by cohort and overall by treatment group using format as specified in [Table 5.4](#) for the safety population.

For each subject it considers all data up to the last recorded dose. For each column, results will be separated for 15 µg/kg, 30 µg/kg, and overall.

For each daily injection, the amount of study treatment taken will be calculated based on the number of units in the syringe pre-injection, minus the number of units remaining in the syringe post-injection. For the cases that the number of units in the syringe pre-injection is not captured in the eCRF, if response to “Was study drug administrated?” is “Yes”, then it will be assumed to be the same as the planned dose; if response to “Was study drug administrated?” is “No”, then it will be assumed to be missing and these records will not be included in the compliance calculation.

The total amount of study treatment taken will be calculated based on the amount of study treatment taken (units) in the corresponding treatment duration.

The total amount of study treatment planned is determined based on the duration of treatment and the planned dose per day.

Percentage compliance for each subject will be derived from the total amount of study treatment intake divided by the planned study treatment intake, and multiplied by 100:

$$\text{Treatment Compliance (\%)} = \frac{\text{Total Amount of Study Drug Taken (units)}}{\text{Total Amount of Study Drug Planned (units)}} \times 100$$

Treatment compliance will be calculated and summarized separately by cohort and overall by treatment group using format as specified in [Table 5.4](#). For each column, results will be separated for 15 µg/kg, 30 µg/kg, and overall.

- Compliance with protocol-specified treatment regimen (%)
- Compliance with protocol-specified treatment regimen (≥50%, ≥60%, ≥70%, ≥80%, ≥90%, ≥100%, ≥110%, ≥120%)

Listings will be provided for compliance.

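### The per-protocol set has an 80% compliance floor but no ceiling, and compliance is a ratio of amounts, so surplus drug can offset missed injections

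*SAP*

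**What the plan says.** The current text is SAP Version 2.0; Section 5.1.2 reads the same in Version 1.1. A PP child is one in the full analysis set who "completed the treatment originally allocated (i.e., always received the assigned treatment (vosoritide or placebo"), and who comes "with a standing height/body length assessment at Week 52 following protocol window, and with treatment compliance of at least 80" per cent. That is the whole definition.

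Section 12 supplies the compliance figure. It is one percentage per child: "Percentage compliance for each subject will be derived from the total amount of study treatment intake divided by the planned study treatment intake". On the period it says: "For each subject it considers all data up to the last recorded dose". The numerator is a sum of units. For the denominator: "The total amount of study treatment planned is determined based on the duration of treatment and the planned dose per day". The tables then report "Compliance with protocol-specified treatment regimen (≥50%, ≥60%, ≥70%, ≥80%, ≥90%, ≥100%, ≥110%, ≥120"%), and results are split by 15 and 30 µg/kg in the summary columns. Section 5.1.2 refers to neither the upper categories nor the split.

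Section 4.2 makes the planned level depend on age: "The dose for all sentinel and randomized subjects in Cohorts 2 and 3 will be adjusted to" 15 µg/kg/day once they turn 24 months, from 30 µg/kg before.

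Section 8 gives major deviations classed as dosing irregularities their own listing. Section 13 counts doses administered and doses missed. Neither is tied to PP membership. Section 14.2.2 names two sensitivity analyses for the primary endpoint, of which PP is one, and Sections 14.3.1 to 14.3.3 carry them over to the key secondary endpoints.

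**The concern.** A PP analysis is meant to show the effect in children treated as the plan intended. Two features of this definition work against that.

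First, the bound is one-sided, so no excess, however large, removes a child. Second, compliance is a ratio of summed amounts, not a count of injections, so surplus on some days cancels missed injections on others.

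The other clauses do not close the gap. The requirement to have always received the assigned treatment is glossed as vosoritide or placebo, so it concerns the arm and not the amount. Read instead as forbidding any missed injection, it would make the 80% floor pointless.

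What is at stake is how one of the two sensitivity analyses is interpreted. If the PP result agrees or disagrees with the primary result, the reader should be able to attribute that to children who followed the regimen.

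**Working it through.** The SAP gives no figure to reproduce here, and Section 4.5 says no formal sample size calculation was made. The check applies Section 12's own formula to illustrative dosing patterns.

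**1. Surplus against missed injections.** Assume 365 planned daily doses (52 weeks, Section 4.2). If a fraction m is missed and the rest are given at s times plan, compliance = (1 − m) × s. The amount per injection needed to reach the floor is s = 0.80 / (1 − m).
- No surplus: 292/365 = 80.0%, so 73 injections may be missed.
- m = 30% (about 110 missed): s = 0.80/0.70 = 114.3%. At s = 115%, compliance is 80.5%, which passes.
- m = 40% (146 missed): s = 0.80/0.60 = 133.3%. At 135%, 81.0%, which passes.
- m = 50% (about 182 missed): s = 0.80/0.50 = 160%, giving 80.0%, which passes.

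**2. Excess alone.** With no injection missed, 150% or 200% of plan every day gives compliance of 150% or 200%. Both pass.

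**3. Illustration from the change of level at 24 months.** Assumptions: 364 days, constant weight and vial concentration, the denominator follows the age-based level, and a child remains on 30 throughout. Taken = 30 × 364 = 10,920. Planned = 30 × d + 15 × (364 − d), where d is the number of days before 24 months.
- Aged 18 months on Day 1 (d = 183): 10,920/8,205 = 133%.
- Aged 21 months (d = 91): 10,920/6,825 = 160%.
- Aged 23 months (d = 30): 10,920/5,910 = 185%.

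All three pass. This can arise only in Cohort 2: Cohort 1 has one level throughout, and Cohort 3 starts treatment below 6 months of age, so it is below 18 months after 52 weeks.

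**4. Weight of one child.** At least 27 + 17 + 17 = 61 are randomized 1:1, so about 30 receive vosoritide, and one child is about 3% of them. Within Cohort 2 alone (17 randomized, 8 or 9 active) one child is 1/9 to 1/8, or 11% to 12.5%.

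**5. Candidate fixes tested on these patterns.**
- A ceiling of 120% alone removes the children in step 2 and all three in step 3, but none of the offset cases in step 1, which lie at 80% to 81%.
- Adding a minimum of 80% of planned injections administered removes the offset cases, since 70%, 60% and 50% were administered.
- Applying 80% to 120% within each dose level does not stop offset inside a level (80.5% still passes) and is unstable for short segments. With 7 planned days at the second level and two missed, 5/7 = 71%, so the child is excluded although overall compliance is above 99%.

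**The case against.** The strongest reply is that little depends on this. The PP set serves sensitivity analyses only, and the primary analysis takes all randomized children in the full analysis set regardless of treatment discontinuation (Section 14.2.1). A one-sided floor contradicts nothing in the SAP. Excess exposure would also be visible elsewhere: compliance is tabulated and listed by dose level, average daily dose is reported, and dosing irregularities are listed. All of this stands and limits the point to a minor one.

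The second reply concerns the illustration. A reader might infer from the categories up to 120% and the age-based change that the SAP expects children to be dosed at twice plan, or that some were. The documents do not support that. The categories are descriptive bins, Section 4.2 says the dose will be adjusted, and nothing shows that any child remained on the other level. This too stands.

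The third reply is that planned is not pinned down. If the denominator comes from the units the site set for that child, one who stayed on 30 would score about 100%, not 133% to 185%, and a ceiling would not see it. This is correct, and is a reason to define the planned amount in the fix.

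What the replies do not remove is that the rule as written admits both patterns and that no other PP clause excludes them.

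**Conclusion.** The point holds in a limited form. By Section 12's formula, the PP definition keeps a child well above plan and a child whose surplus hides missed injections; 30% missed with the rest at 115% is enough. That follows from the text and needs no assumption about the change of level at 24 months.

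The 133%, 160% and 185% figures are illustrations only and rest on the assumptions in step 3. The number of children affected is unknown. One affected child would be about 3% of the active children overall, more in a Cohort 2 analysis on its own.

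It would be wrong to conclude that the primary result is biased or that over-dosing took place; nothing in the documents shows either. Minor severity: a cheap improvement.

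**What to change.** In Section 5.1.2, replace the floor with two conditions: overall compliance between 80% and 120% (the SAP's own top reporting category), and at least 80% of planned injections administered, from the administered and missed dose counts in Section 13. In Section 12, state that the planned amount is the level planned for the child's age under Section 4.2, with the Cohort 2 sentinel escalation described there taken into account. Do not apply the band to each dose level separately unless a minimum segment length is set.

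Some patterns remain. A child on 30 throughout who turned 24 months three quarters of the way through would score 30/26.25 = 114.3% and stay in. So would a child with equal halves at each level who took 60% of injections in the first half and all of them at twice plan in the second: 80% administered and 106.7% overall. Catching these would need the per-level rule with a minimum segment length, and the gain looks small.

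The cost is a sentence in each section and a short derivation from data already planned. The PP set may lose some children. The primary analysis is unchanged, and the change defines an analysis set only; it implies no dosing rule.
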